## Sample size calculation

As the primary outcome in this study is willingness to pay (WTP), this has been used to calculate the sample size. Differences in mean and median WTP values between the three forms of information are therefore the primary driver of sample size. Lancsar & Louviere (2008) highlight the complexities and problems of performing sample size calculations for stated preference surveys such as discrete choice experiments and contingent valuation studies (Lancsar & Louviere, 2008). In particular, the parameters that will be estimated by the CV survey (willingness to pay) must be known in advance in order to conduct a useful sample size calculation – information we do not have in advance of conducting this work. Previous studies however, using CV in health care settings have included samples ranging from less than 50 to over 1000 respondents. Recent CV work in dentistry has also used similar sizes (between 36 and 200 per group), albeit looking at treatments rather than provision of information (Rosvall et al., 2009). So, we believe that a sample size of 400 i.e. 133 in each group will be adequate in this case.

Whilst WTP is the primary outcome measure, and sample size calculation was done on this basis, we have however calculated the implications of this sample size for the detection of secondary (clinical) outcome effects. Thus we have also carried out a sample size calculation using the secondary outcome of plaque percent index (PPI), (measured using QLF). Published data on a group of 38 college students showed a mean PPI of 14.8, with a standard deviation of 7.7 (Aleksejuniene et al., 2006). As this is likely to be a more homogeneous population than in this study, we can use a more conservative estimate of s.d. of 10, to calculate that a sample size of 133 per group would allow us to detect a mean difference of 3.5 in PPI between groups, with 80% power, at the 0.05 significance level.

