# Literacy (V1)

 Patients' literacy (Using the Rapid Estimate of Adult Literacy in Medicine - REALM-R), Bass (2003): collected by a dental nurse using a laminated sheet of the 8 REALM medical words (including 3 practice words, with the American spelling of anemia substituted for the English spelling anaemia).

Dental visiting and previous dental experiences (V1). Four items were taken from the Adult Dental Health Survey, 2009 (Health and Social Care Information Centre, 2011).

- In general do you go to the dentist for: a regular check-up/an occasional checkup/only when having trouble with my teeth/dentures?
- How many times have you been to the dentist in the last five years purely for a checkup?
- We would like to know about the types of dental care/treatment that you have received from dentists over the course of your whole life. This includes any care or treatment you may have had as a child (Have you ever had fillings/teeth extracted (taken out)/a dental bridge or a tooth crowned/a root canal treatment/a scale and polish?)
- We included an additional question on pain experience: Have you ever experienced dental pain bad enough to make you go to the dentist (tick all that apply): 1=currently in pain, 2=In the last 6 months, 3=6 months to 2 years ago, 4=more than 2 years ago, 5=never).
- Number of failed appointments in the course of the study (from recruitment log records)

Dental Anxiety (MDAS): (V1). The Modified Dental Anxiety Scale (Humphris, et al, 1995) consists of 5 questions relating to how the patient would feel about various aspects of dental treatment if it were to happen tomorrow. For each item there is a 5 category rating scale, ranging from 'not anxious' to 'extremely anxious'.

Self-assessed oral health: (V1, V2, V3, F1, F2) using one item and a 5 point Likert scale: *Would you say your dental health (mouth, teeth and/or dentures) is*: 1=very good, 2=good, 3=fair, 4=poor, 5=very poor was derived from the Adult Dental Health Survey, 2009 (Health and Social Care Information Centre, 2011).

b) Dentists' characteristics collected at V1

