## Comparing clinical outcomes between the three intervention arms

Comparison of QLF outcomes between the three groups will use a repeated measures mixed model approach. These models allow for analysis of multiple measurements within each participant. In this case each QLF outcome will be measured at three time-points. The first time-point is the baseline measurement, and the measurement taken here will be used as a covariate in the final model. The repeated measures approach allows us to analyse both follow-up measures (V2 and V3) together, while adjusting for the correlation of repeated measurements within participants. Using a mixed model approach, rather than a repeated measures ANOVA, allows for flexibility in the event of missing data, and can adjust for multiple covariates in the model. If there is a high level of missing data, a multiple imputation approach will be used to assess the robustness of the results. Using all the data which is available, 5 complete case data sets will be imputed, and each analysed in the same way. The results can then be combined, and compared with the analysis excluding missing data, to assess whether this would be likely to change the overall conclusions.

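### Fixing five imputations for heavily missing QLF data makes a borderline sensitivity result hard to reproduce, and the check does not test data missing not at random

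*Protocol*

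**What the plan says.** The relevant text is the protocol section on comparing clinical outcomes between the three intervention arms.

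- **Main analysis.** "Comparison of QLF outcomes between the three groups will use a repeated measures mixed model approach". V2 and V3 are analysed together with the baseline value as a covariate. The approach is preferred to repeated measures ANOVA because it "allows for flexibility in the event of missing data, and can adjust for multiple covariates in the model".
- **Trigger and purpose of imputation.** "If there is a high level of missing data, a multiple imputation approach will be used to assess the robustness of the results".
- **Method.** "Using all the data which is available", the section continues, "5 complete case data sets will be imputed, and each analysed in the same way".
- **Use of the result.** The pooled result is "compared with the analysis excluding missing data, to assess whether this would be likely to change the overall conclusions".

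The section names no missingness assumption and describes no other sensitivity analysis for missing QLF data. The protocol gives no expected dropout rate.

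**The concern.** Two things are fixed here that work against the stated purpose.

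1. **The number of imputations.** Simulation noise in a pooled result grows with the fraction of missing information and shrinks with the number of imputations. The plan sets that number at five and runs the method only when missingness is high, which is where five is least adequate. A sensitivity result near the significance boundary could then change with the random seed.

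2. **What the comparison varies.** A likelihood mixed model already uses participants with incomplete follow-up and is valid when data are missing at random. Standard imputation from the same variables, followed by the same model, makes essentially the same assumption. Agreement is then expected, and it is silent on whether those who miss V2 or V3 have more plaque than their observed data predict. At stake is a statement of robustness that covers less than a reader would take from it.

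**Working it through.** **Reproducing the plan's own figure.** The sample size section states that "a sample size of 133 per group would allow us to detect a mean difference of 3.5 in PPI between groups", with SD 10, 80% power and 0.05 significance (taken as two-sided). Detectable difference = (1.960 + 0.842) × 10 × √(2/133) = 3.44. Power at 3.5 is 81.4%. The stated figure is confirmed, so 3.5 PPI points is a fair yardstick below.

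**Noise from the number of imputations.** Inputs: m = 5 (protocol); m = 50 for comparison; fraction of missing information (FMI) of 0.1, 0.3 and 0.5, assumed because the protocol gives no dropout rate.

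- Seed-to-seed SD of z ≈ √(FMI/m). For example, √(0.3/5) = 0.24 and √(0.3/50) = 0.08.
- Reference degrees of freedom = (m − 1)/FMI². For example, 4/0.09 = 44.
- Relative efficiency = 1/(1 + FMI/m). For example, 1/1.06 = 0.943.

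| FMI | SD of z, m=5 | SD of z, m=50 | df, m=5 | df, m=50 | Efficiency, m=5 | Efficiency, m=50 |
|---|---|---|---|---|---|---|
| 0.1 | 0.14 | 0.04 | 400 | 4900 | 0.980 | 0.998 |
| 0.3 | 0.24 | 0.08 | 44 | 544 | 0.943 | 0.994 |
| 0.5 | 0.32 | 0.10 | 16 | 196 | 0.909 | 0.990 |

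A slightly stricter form, √(FMI/(m + 1)), gives 0.13, 0.22 and 0.29 for m = 5, which leads to the same reading. For a z that would settle at 1.96 with unlimited imputations, the 95% band over seeds at FMI 0.3 is 1.96 ± 1.96 × 0.24, or about 1.5 to 2.4. With m = 50 it is 1.96 ± 1.96 × 0.08, or about 1.8 to 2.1.

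**Simulation check.** Set-up: 133 per arm, SD 10, one follow-up, baseline correlation 0.5 (assumed), data missing completely at random, and imputation on the same variables as the analysis.

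- On one data set with 30% missing, the 5th to 95th percentile of the p-value over repeated runs was 0.034 to 0.239 with m = 5 and 0.070 to 0.131 with m = 50. With 10% missing it was 0.027 to 0.080 and 0.034 to 0.051.
- With a true difference of 3.5, the chance that two runs on the same data disagree about p < 0.05 was:

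| Missing | m=5 | m=50 |
|---|---|---|
| 10% | 5% | 1% |
| 20% | 8% | 1% |
| 30% | 16% | 3.5% |
| 40% | 21% | 3.5% |

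**Same assumption.** In the 30% data set the estimate without imputation was −2.17. The average over imputation runs was −2.17 with m = 5 and −2.16 with m = 50. On the same variables, imputation reproduced the estimate and added only noise.

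**Size of an undetected departure (illustrative).** If the missing patients in one arm are d PPI points worse than predicted, the arm difference is biased by (proportion missing) × d. For d = 5:

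- 20% missing: 0.20 × 5 = 1.0, and 1.0/3.5 = 29% of the design difference.
- 30% missing: 0.30 × 5 = 1.5, and 1.5/3.5 = 43%.

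For d = 2 the biases are 0.4 (11%) and 0.6 (17%). If both arms have the same proportion missing and the same d, the bias cancels, so one-arm shifts must be examined as well as a common shift.

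**The case against.** A reader might infer that the planned imputation is unstable and cannot show robustness at all. The documents do not support that, for these reasons.

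- Missing at random is inferred from the methods, not stated. The instruction to use all available data leaves room for auxiliary variables. The protocol collects candidates: self-reported hygiene at every contact and, in the Measures section, "Number of failed appointments in the course of the study". With these in the imputation model, the two analyses condition on different information and could differ. Imputation could also bring back participants whom the mixed model drops, such as those without a baseline image.
- Baseline QLF is already a covariate, so poor cleaning visible at V1 is handled. Only worsening beyond what the observed data predict would escape.
- QLF follow-up ends about 4 to 6 weeks after V1, so missingness may be low. Near 10% missing, the noise from five imputations is modest.
- Efficiency stays at 91% or more, and the pooled degrees of freedom already allow for a small number of imputations. The defect is in reproducibility, not validity.
- Only a conditional sensitivity analysis of secondary outcomes is touched. The mixed model involves no seed, and hypothetical willingness to pay, the primary outcome, is collected at V1.

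All of this stands as a limit on the point. A reader might also count the undefined trigger and the unlisted imputation variables as errors. Both are details that an SAP may properly supply, so neither is a finding alone. What the objection does not remove is that the protocol itself fixes five imputations and assigns them the robustness role. Nor do auxiliary variables supply an analysis in which data are missing not at random.

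**Conclusion.** The point holds in a limited form. With five imputations the seed-to-seed SD of z is about 0.14, 0.24 and 0.32 at an FMI of 0.1, 0.3 and 0.5, roughly three times its value with 50. A borderline sensitivity result under substantial missingness may therefore not be reproducible. Unless auxiliary variables are added, the comparison leaves the missingness assumption essentially unchanged. In either case it cannot show robustness to data missing not at random.

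The FMI values, the missing proportions and the 5-point departure are assumptions, since the documents give no dropout rate. The main QLF result and the primary outcome are unaffected. Priority is low to moderate.

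**What to change.** 1. Replace the fixed five with a number scaled to the missing fraction. One workable rule is to keep √(FMI/m) at or below 0.1, so that m ≥ 100 × FMI: 10, 30 and 50 at FMI 0.1, 0.3 and 0.5. Fixing 50 covers that whole range.
2. Add a shift analysis for PPI. Worsen the imputed values by a range of amounts (for example 1 to 5 points), first in all arms and then in one arm at a time. Report the shift at which the conclusion changes.
3. While editing, say whether the comparator described as excluding missing data is the mixed model, which uses incomplete participants, or a complete-case analysis.

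The cost is minutes of computing and a few lines of analysis text. No data collection changes.

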## The cost-benefit framework analysis

The valuation data will be most meaningful if compared to costs. Although a cost-benefit analysis would be the ideal way of combining costs and benefits in a meaningful way, a robust cost benefit analysis of oral health risk information would entail modelling changes in disease levels resulting from behaviour change linked to the information given. In turn, it would be important to understand the lifetime (or certainly long term) consequences in terms of costs and benefits of changing disease levels. This would result in a hugely complex model, for which we have very little (and in many areas, no) evidence or data. Such a robust full scale cost-benefit analysis is therefore impossible not possible. We therefore propose to undertake a more limited outline cost-benefit framework analysis.

Thus WTP data will be combined with a cost-benefit framework analysis. The principal outcome of any such analysis would be net benefit or cost in monetary terms (i.e. £). Given that cost-benefit analysis expresses both costs and benefits in commensurate units the decision rule for cost-benefit analysis is therefore relatively simple. If the benefits (measured in £ via WTP) exceed the costs (also measured in £) this represents a gain in welfare and the strategy deemed worthwhile (Drummond et al., 1997). The level of complexity of this analysis will depend on the data available in the literature concerning longer term effects of

risk information and oral health behaviour change on oral health. The cost-benefit framework analysis will also give an indication of the likely effect of any sustained behaviour change. Data from the endpoint of the study (12 months) will be used to illustrate the effect of the behaviour change resulting for the different interventions at this time point. Results will be presented as incremental net benefits (net benefits = mean WTP – mean cost of intervention).

